### 7.2.3. Asthma Control Endpoints

The asthma control secondary endpoints are:

- Change from baseline (Randomisation) in ACT total score at Month 6 (Visit 10), measured at baseline (Visit 2, 3 or 4) and Month 6 (Visit 10)
- Percentage of patients becoming controlled as defined as an Asthma Control Test score  $\geq 20$  at Month 6 (Visit 10)
- Percentage of patients with an increase from baseline  $\geq 3$  in ACT total score at Month 6 (Visit 10)
- Percentage of patients who have either an ACT total score of  $\geq 20$  and/or an increase from baseline of  $\geq 3$  in ACT total score at Month 6 (Visit 10)

#### 7.2.3.1. Summary Measure

The asthma control summary measures are:

- The difference in LS means of the change from baseline in ACT total score at month 6, along with a 95% confidence interval and p-value for the difference, analysed using an MMRM model.
- An adjusted odds ratio on percentage of patients becoming controlled as defined as an ACT total score  $\geq 20$  at Month 6, along with a 95% confidence interval and p-value for the percentage, analysed using a logistic regression model.
- An adjusted odds ratio on percentage of patients with an increase from baseline  $\geq 3$  in ACT total score at Month 6, along with a 95% confidence interval and p-value for the percentage, analysed using a logistic regression model.
- An adjusted odds ratio on percentage of patients who have either an ACT total score of  $\geq 20$  and/or an increase from baseline of  $\geq 3$  in ACT total score at Month 6, along with a 95% confidence interval and p-value for the percentage, analysed using a logistic regression model.

### 7.2.3.2. Population of Interest

The asthma control analyses will be based on the Intent-to-Treat population.

### 7.2.3.3. Strategy for Intercurrent (Post-Randomisation) Events

Intercurrent events for the asthma control outcomes were identified as:

- Early discontinuation of ELLIPTA
- Early discontinuation of the APP
- Early discontinuation of ELLIPTA sensor
- Early discontinuation of MDI sensor
- Early withdrawal from study
- Use of MDI rescue medication
- Use of prohibited medications
- Change of dose of ELLIPTA

The “Treatment policy” strategy will be applied to handle the “Early discontinuation of ELLIPTA sensor”, “Early discontinuation of the APP”, “Early discontinuation of MDI sensor”, “Use of MDI rescue medication”, “Use of prohibited medications” and “change of dose of ELLIPTA” for all asthma control exploratory endpoints. The strategy implies direct use of ACT data irrespective of the occurrence of these intercurrent events.

#### 7.2.3.3.1. Change from baseline (Randomisation) in ACT total score at Month 6 (Visit 10)

The “treatment policy” strategy will be applied to all handle all the intercurrent events listed in Section 7.2.3.3 Strategy for Intercurrent (Post-Randomisation) Events. In other words, all observed data before early discontinuation of the study respective of treatment arm status (on-treatment) or CIS discontinuation status will be included in the analysis. No missing data will be imputed, missing data will be considered MAR. Therefore, the primary treatment arm effect to be estimated will be the mean change from baseline in ACT total score at month 6 and remaining on study.

#### 7.2.3.3.2. Percentage of patients becoming controlled as defined as an Asthma Control Test score $\geq 20$ at Month 6 (Visit 10)

The “Composite” strategy will be used for the “Early discontinuation of ELLIPTA” and ‘Early discontinuation of study’ intercurrent events. In the occurrence of these intercurrent events, the effect to be estimated will be the effect on the outcome of achieving an ACT total score of  $\geq 20$  at month 6 and remaining on ELLIPTA (off-ELLIPTA treatment data is not collected). Participants who do not meet the improvement threshold, have missing values for their ACT total score at month 6, or prematurely discontinue using ELLIPTA or the study will be classified as non-responders in all planned analyses for this endpoint.

The “Treatment policy” strategy will be used to handle discontinuation of the APP/sensor. This means direct assessment of ACT total score at month 6 against the responder criteria, irrespective of CIS discontinuation status.

### **7.2.3.3.3. Percentage of patients with an increase from baseline $\geq 3$ in ACT total score at Month 6 (Visit 10)**

The “Composite” strategy will be used for the “Early discontinuation of ELLIPTA” and ‘Early discontinuation of study’ intercurrent events. In the occurrence of these intercurrent events, the effect to be estimated will be the effect on the outcome of achieving an increase from baseline of  $\geq 3$  in ACT total score at month 6 and remaining on ELLIPTA (off-ELLIPTA treatment data is not collected). Participants who do not meet the improvement threshold, have missing values for their ACT total score at month 6, or discontinue using ELLIPTA or the study will be classified as non-responders in all planned analyses for this endpoint.

The “Treatment policy” strategy will be used to handle discontinuation of the APP/sensor. This means direct assessment of ACT total score at month 6 against the responder criteria, irrespective of CIS discontinuation status.

### **7.2.3.3.4. Percentage of patients who have either an ACT total score of $\geq 20$ and/or an increase from baseline of $\geq 3$ in ACT total score at Month 6 (Visit 10)**

The “Composite” strategy will be used for the “Early discontinuation of ELLIPTA” and ‘Early discontinuation of study’ intercurrent events. In the occurrence of these intercurrent events, the effect to be estimated will be the effect on the composite outcome of achieving an ACT total score of  $\geq 20$  and/or an increase from baseline of  $\geq 3$  in ACT total score at month 6 and remaining on ELLIPTA (off-ELLIPTA treatment data is not collected). Participants who do not meet the improvement threshold, have missing values for their ACT total score at month 6, or discontinue using ELLIPTA during or the study will be classified as non-responders in all planned analyses for this endpoint.

The “Treatment policy” strategy will be used to handle discontinuation of the APP/sensor. This means direct assessment of ACT total score at month 6 against the responder criteria, irrespective of CIS discontinuation status.

### **7.2.3.4. Statistical Analyses / Methodology Specification**

Details of the planned displays will be provided in [10.8 Appendix 8: List of Data Displays](#) and will be based on GSK data standards and statistical principles.

Unless otherwise specified, endpoints/variables defined in Section [7.2.3.1](#) Summary Measure will be summarised using descriptive statistics, graphically presented (where appropriate) and listed.

### 7.2.3.4.1. Change from baseline in ACT total score at month 6

Endpoint / Variables
Change from baseline in ACT total score Month 6 (visit 10)
Model Specification

This endpoint will be analysed using a mixed model repeated measures (MMRM) model utilising the REML estimation approach and the default unstructured covariance matrix structure. Whilst missing data are not implicitly imputed in this analysis, there is an underlying assumption that the data are MAR. All non-missing data for a participant will be used within the analysis and, via modelling of the within-participant correlation structure, the derived treatment differences will be adjusted to take into account missing data.

Terms fitted in the model will include:
 
 
Dependent Variable: change from baseline in ACT total score
 
Covariates: 
 
Fixed categorical: randomised treatment arm, visit (month 1 and 6), gender and country.
 
Fixed continuous: baseline ACT total score and age
 
Interaction terms: randomised treatment arm-by-visit, baseline ACT total score-by-visit
 
Random effect: participant
 
 
 

Model Checking & Diagnostics

 
If this model fails to converge, alternative correlation structures may be considered
 
Appropriate graphs will be reviewed as part of the model checking process to ensure that distributional assumptions hold. These will include a normal probability plot of the residuals and a plot of the residuals versus the fitted values (checking the normality assumption and constant variance assumption of the model, respectively).
 
Interactions with treatment will be explored for other model covariates and tests for interactions will be at the 2-sided 10% significance level. Any significant interactions that are found will be thoroughly investigated and where necessary, extra outputs will be produced.
 

Model Results Presentation
Adjusted mean change from baseline values for each treatment arm will be presented with their associated standard errors. The estimated treatment difference along with corresponding standard error, 95% confidence interval (CI) and p-value will be presented for the treatment comparisons at month 6 (Visit 10).

### 7.2.3.4.2. ACT total score $\geq 20$ at month 6

Endpoint / Variables
Percentage of patients becoming controlled as defined as an Asthma Control Test score $\geq 20$ at Month 6 (Visit 10)
Model Specification

This endpoint will be analysed using a logistic regression model. Only the month 6 (visit 10) data will be included in the model. Month 1 (visit 5) data will not be implemented since by this timepoint participants may not have reverted to steady medicating behaviour.

Will not be included since participants may not have reverted to normally medicating practise within one month's use of the CIS/

Terms in the model:
 
 
Dependent variable: ACT total score <math>\geq 20</math> responder/non-responder at month 6 (binary score)
 

- Covariates:
  - Categorical: randomised treatment arm, gender and country
  - Continuous: baseline ACT total score and age.

Patients who have a missing ACT total score at month 6 (visit 10) (i.e. no ACT data on-treatment) will be classified as non-responders at that visit.

Computation of confidence intervals for the odds ratios is based in the individual Wald tests.

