## Summary of Total Rescue Use as Determined by the Maintenance Sensor

Month		Arm 1 (N=xxx)	Arm 2 (N=xxx)	Arm 3 (N=xxx)	Arm 4 (N=xxx)	Arm 5 (N=xxx)
Baseline	n	XX	XX	XX	XX	XX
	Mean	XX.X	XX.X	XX.X	XX.X	XX.X
	SD	X.XX	X.XX	X.XX	X.XX	X.XX
	Median	XX.X	XX.X	XX.X	XX.X	XX.X
	Min.	XX	XX	XX	XX	XX
	Max.	XX	XX	XX	XX	XX
Month 1	n	XX	XX	XX	XX	XX
	Mean	XX.X	XX.X	XX.X	XX.X	XX.X
	SD	X.XX	X.XX	X.XX	X.XX	X.XX
	Median	XX.X	XX.X	XX.X	XX.X	XX.X
	Min.	XX	XX	XX	XX	XX
	Max.	XX	XX	XX	XX	XX
Average Month 1 to 6	n	XX	XX	XX	XX	XX
	Mean	XX.X	XX.X	XX.X	XX.X	XX.X
	SD	X.XX	X.XX	X.XX	X.XX	X.XX
	Median	XX.X	XX.X	XX.X	XX.X	XX.X
	Min.	XX	XX	XX	XX	XX
	Max.	XX	XX	XX	XX	XX

Programming note: Continue table to include all monthly timelines (month 2, month 3, month 4, month 5, month 6, average month 4-6)

Example : EFF\_T1

Protocol : 207040

Population : Intent-to-Treat

Page 1 of x

Table 2.xx  
Summary of Asthma Control Test (ACT) Total Score

Visit		Arm 1 (N=xxx)	Arm 2 (N=xxx)	Arm 3 (N=xxx)	Arm 4 (N=xxx)	Arm 5 (N=xxx)
Baseline [1]	n	XX	XX	XX	XX	XX
	Mean	XX.X	XX.X	XX.X	XX.X	XX.X
	SD	X.XX	X.XX	X.XX	X.XX	X.XX
	Median	XX.X	XX.X	XX.X	XX.X	XX.X
	Min.	XX	XX	XX	XX	XX
	Max.	XX	XX	XX	XX	XX
Visit 5 (Month 1)	n	XX	XX	XX	XX	XX
	Mean	XX.X	XX.X	XX.X	XX.X	XX.X
	SD	X.XX	X.XX	X.XX	X.XX	X.XX
	Median	XX.X	XX.X	XX.X	XX.X	XX.X
	Min.	XX	XX	XX	XX	XX
	Max.	XX	XX	XX	XX	XX
Change from Baseline at Visit 5 (Month 1)	n	XX	XX	XX	XX	XX
	Mean	XX.X	XX.X	XX.X	XX.X	XX.X
	SD	X.XX	X.XX	X.XX	X.XX	X.XX
	Median	XX.X	XX.X	XX.X	XX.X	XX.X

[1] Baseline ACT total score is taken at randomisation visit.

*Programming note: repeat for Visit 10 (Month 6), Change from Baseline at Visit 10 (Month 6), Early Withdrawal, Change from Baseline at Early withdrawal*

Example : EFF\_T4

Protocol : 207040

Population: Intent-to-Treat

Page 1 of 1

Table 2.xx

Summary of the Statistical Analysis of Change from Baseline (Randomisation) in ACT Total Score at Visit 10 (Month 6)

	Arm 1 (N=xxx)	Arm 2 (N=xxx)	Arm 3 (N=xxx)	Arm 4 (N=xxx)	Arm 5 (N=xxx)
n	xx	xx	xx	xx	xx
LS Mean Change (SE)	xx.xx (x.xxx)				
CIS Arm vs. Arm 5					
Difference	xx.x	xx.x	xx.x	xx.x	xx.x
95% CI	(xx.x, xx.x)	(xx.x, xx.x)	(xx.x, xx.x)	(xx.x, xx.x)	
p-value	x.xxx	x.xxx	x.xxx	x.xxx	

Note: The analysis method was an MMRM adjusted for randomised treatment arm, (visit), baseline ACT total score, randomised treatment arm-by-visit interaction, baseline ACT total score-by-visit interaction, gender, age, country and subject fitted as a random factor.

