Note: The Restricted Maximum Likelihood (REML) estimation approach was used with a default covariance structure of unstructured.

Programming note: Should computational issues be encountered when using an unstructured covariance structure, other structures including AR1 and CS should be considered and the second footnote updated as appropriate.

Example : EFF\_T12  
 Protocol : 207040  
 Population : Intent-to-Treat

Page 1 of 1

Table 2.xx

Summary of Percentage of Subjects Who Have Either an ACT Total Score of  $\geq 20$  and/or  $\geq 3$  Point Increase from Baseline (Randomisation) in ACT Total Score

Visit		Arm 1 (N=xxx)	Arm 2 (N=xxx)	Arm 3 (N=xxx)	Arm 4 (N=xxx)	Arm 5 (N=xxx)
Visit 5 (Month 1)	n	xxx	xxx	xxx	xxx	xxx
	ACT Total Score $\geq 20$ and/or $\geq 3$ Point Increase from Baseline	xxx (xx%)				
	ACT Total Score $\geq 20$	xxx (xx%)				
	$\geq 3$ Point Increase from Baseline	xxx (xx%)				
Visit 10 (Month 6)	n	xxx	xxx	xxx	xxx	xxx
	ACT Total Score $\geq 20$ and/or $\geq 3$ Point Increase from Baseline	xxx (xx%)				
	ACT Total Score $\geq 20$	xxx (xx%)				
	$\geq 3$ Point Increase from Baseline	xxx (xx%)				

Example : EFF\_T13  
 Protocol : 207040  
 Population : Intent-to-Treat

Page 1 of 1

Table 2.xx  
 Summary of the Statistical Analysis of Percentage of Subjects Who Have an ACT Total Score of  $\geq 20$  at Visit 10 (Month 6)

	Arm 1 (N=xxx)	Arm 2 (N=xxx)	Arm 3 (N=xxx)	Arm 4 (N=xxx)	Arm 5 (N=xxx)
n	xxx	xxx	xxx	xxx	xxx
Responder [1]	xxx (xx%)				
Non-Responder	xxx (xx%)				
CIS Arm v Arm 5					
Adjusted Odds Ratio	x.xx	x.xx	x.xx	x.xx	
95% C.I.	(x.xx, x.xx)	(x.xx, x.xx)	(x.xx, x.xx)	(x.xx, x.xx)	
p-value	x.xx	x.xx	x.xx	x.xx	

[1] Responder is defined as an ACT total score  $\geq 20$ .

Note: The analysis method was logistic regression adjusted for randomised treatment arm, baseline ACT total score, country, gender and age

Example : EFF\_T13  
 Protocol : 207040  
 Population : Intent-to-Treat

Page 1 of 1

Table 2.xx

Summary of the Statistical Analysis of Percentage of Subjects with an Increase from Baseline (Randomisation)  $\geq 3$  in ACT Total Score at Visit 10 (Month 6)

	Arm 1 (N=xxx)	Arm 2 (N=xxx)	Arm 3 (N=xxx)	Arm 4 (N=xxx)	Arm 5 (N=xxx)
n	xxx	xxx	xxx	xxx	xxx
Responder [1]	xxx (xx%)				
Non-Responder	xxx (xx%)				
CIS Arm v Arm 5					
Adjusted Odds Ratio	x.xx	x.xx	x.xx	x.xx	
95% C.I.	(x.xx, x.xx)	(x.xx, x.xx)	(x.xx, x.xx)	(x.xx, x.xx)	
p-value	x.xx	x.xx	x.xx	x.xx	

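### The ACT, ASUI and SGRQ repeated-measures models carry a redundant random participant effect, and the two named fallback structures keep it while adding an equal-variance restriction

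*SAP*

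**What the plan says.** SAP 7.2.3.4.1 (ACT) specifies a "mixed model repeated measures (MMRM) model utilising the REML estimation approach and the default unstructured covariance matrix structure". Its categorical terms include "visit (month 1 and 6), gender and country", so each participant contributes at most two post-baseline values. The same list of terms ends with "Random effect: participant". Sections 7.3.3.5.2 (ASUI) and 7.3.3.5.4 (SGRQ) give the same three elements.

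The Appendix 9 table shells for these analyses repeat them in two separate footnotes. The first lists the model terms and closes with "gender, age, country and subject fitted as a random factor"; the second states REML with an unstructured default.

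On what to do if the fit fails, section 7.2.3.4.1 says only: "If this model fails to converge, alternative correlation structures may be considered". The programming notes under the three shells are more specific: "Should computational issues be encountered when using an unstructured covariance structure, other structures including AR1 and CS should be considered". They ask for the second footnote alone to be updated, so the random subject in the first footnote stays.

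**The concern.** An unstructured matrix on two visits already describes the within-participant covariance completely. A participant variance on top has nothing left to estimate. Software given both terms may stop, warn of a Hessian that is not positive definite, or set one term to zero. The plan offers a change of correlation structure in response to such trouble, but the structures it names keep the redundant term and so cannot cure it.

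At stake is the Month 6 standard error, and with it the confidence interval and p-value that the SAP reports for each arm against Arm 5. A move to AR1 or CS would come after a failed fit, would have no statistical reason behind it, and would impose equal variance at Months 1 and 6.

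**Working it through.** The documents state no figure for these models, so there is none to reproduce. The check is a parameter count, an illustration on simulated data, and the size of the fallback's effect.

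**Inputs from the SAP.** Two visits; unstructured (UN) residual covariance R; a participant random intercept with variance τ²; named fallbacks AR1 and CS with the random intercept kept.

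**Parameter count.** The marginal covariance is V = R + τ²J, where J is the 2×2 matrix of ones. V has three distinct elements: V11, V12 and V22.

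- UN + participant: V11 = r11 + τ², V12 = r12 + τ², V22 = r22 + τ². Any change in τ² is absorbed by subtracting the same amount from every element of R.
- CS + participant: V11 = V22 = σ² + c + τ², V12 = c + τ². Only two distinct elements remain, and c and τ² enter only as a sum.
- AR1 + participant: V11 = V22 = σ² + τ², V12 = σ²ρ + τ². With one lag, AR1 alone is one variance and one covariance, which is the same marginal model as CS.

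The rank of the map from parameters to (V11, V12, V22), computed numerically, agrees:

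| Structure | Alone: parameters / rank | With random participant: parameters / rank |
|---|---|---|
| UN | 3 / 3 | 4 / 3 |
| CS | 2 / 2 | 3 / 2 |
| AR1 | 2 / 2 | 3 / 2 |
| Heterogeneous AR1 | 3 / 3 | 4 / 3 |

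**Illustration.** Two-visit data were simulated for 5 arms of 86, with assumed variances 12 and 16, covariance 6, and 10% missing at Month 6.

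- UN with τ² set to 0, 1, 3, 5 and 8: −2 REML log-likelihood is 2909.540 every time. The Month 6 difference is 1.176 with SE 0.640 every time, the same as UN alone.
- AR1 and CS with τ² set to 0, 1, 3 and 5: 2914.914 every time, for both structures. The difference is 1.186 with SE 0.606.

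So the likelihood is flat in τ², but the reported contrast does not move along the flat direction. It moves when the structure changes: 0.606/0.640 = 0.947.

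**Size of the fallback's effect.** Under equal variances the Month 6 variance is replaced by roughly the mean of the two visit variances. With r = (Month 6 variance)/(Month 1 variance), the SE relative to UN is about √[(1 + 1/r)/2]. The documents give no SD of change for any of the three scores, so r is an assumption:

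| r | SE under AR1 or CS ÷ SE under UN |
|---|---|
| 0.67 | 1.12 |
| 0.8 | 1.06 |
| 1.0 | 1.00 |
| 1.25 | 0.95 |
| 1.5 | 0.91 |
| 2.0 | 0.87 |

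The illustration's fitted variances, 12.68 and 15.74, give r = 1.24 and a predicted ratio of 0.95, in line with the 0.947 found.

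**The case against.** The strongest reply is that nothing the SAP reports is unidentified. Only the split between participant variance and residual covariance is. Section 7.2.3.4.1 reports adjusted means, differences, standard errors, intervals and p-values, and no variance components. If software sets the redundant variance to zero, the output is what the corrected model would give. This stands. A reader might infer from the parameter count that the treatment effect cannot be estimated, and the working shows otherwise.

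The harm also needs several steps: the random term is coded literally beside the unstructured matrix, the fit then misbehaves, the analyst chooses AR1 or CS, and the two visit variances differ. This also stands, so the consequence is possible rather than certain. The fallback list is open as well, since the shells speak of structures "including" these two. AR1 and CS are the only ones named, but heterogeneous structures are not ruled out. The section text is triggered by non-convergence only, although the shells' reference to computational issues is broader.

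It could be said that the random effect is loose wording for the subject of the repeated measures. The shells make this hard to sustain, because they state the random subject and the covariance structure in separate footnotes and tell the programmer to change only one of them.

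Finally, SAP 2.4 describes the secondary comparisons as descriptive, and the ASUI and SGRQ mean changes are exploratory. That limits the importance of the point but does not make the specification correct.

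**Conclusion.** The specification is wrong as written for all three models, and the two named fallbacks do not repair it. The count is exact: four covariance parameters for three elements under UN, and three for two under AR1 or CS. It needs no assumption beyond the two visits and the terms the SAP lists.

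The consequence is conditional. The Month 6 differences and standard errors are sound if the redundant variance is dropped or set to zero. If a computational failure leads to AR1 or CS, the Month 6 SE could be about 13% too small to 12% too large, for assumed variance ratios of 2.0 to 0.67.

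Two stronger readings are not supported. One is that the Month 6 SE would be too small: that holds only if variance is larger at Month 6, and the documents give no SDs to say so. The other is that Hessian-based degrees-of-freedom corrections would fail: the SAP names no such correction for these models. The primary adherence ANCOVA is not affected. The change is worth making because it costs almost nothing and removes a built-in cause of a failed fit.

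**What to change.** Delete the random participant effect from the term lists in SAP 7.2.3.4.1, 7.3.3.5.2 and 7.3.3.5.4, and the random subject from the first footnote of the three corresponding Appendix 9 shells. Keep participant only as the subject within which the unstructured residual covariance applies.

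In the three programming notes, replace AR1 and CS with a structure that allows different variances at Months 1 and 6, and refer to it in the section text so that the two places agree. Say openly that on two visits heterogeneous CS is the unstructured matrix in another parameterisation: it may help the optimiser, but it is not a simpler model.

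The cost is wording in three sections and three shells. The code becomes shorter, no data or endpoint changes, and nothing is lost, because the unstructured model alone gives the same estimate and SE.

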#### Model Checking & Diagnostics

If the likelihood maximisation algorithm fails to converge due to complete or quasi-complete separation of the data then Firth's penalized likelihood ([Firth](#), 1993) will be implemented by use of the FIRTH option on the MODEL statement in PROC LOGISTIC.

The fit of the logistic regression model will be assessed by examining the ROC curve and other diagnostic plots

#### Model Results Presentation

The number and percentage of participants with a response within each randomised treatment arm will be presented by visit, together with the adjusted odds ratio comparing CIS Arms 1, 2, 3, 4 with Arm 5, associated 95% CIs and p-values.

### 7.2.3.4.3. Increase from Baseline of $\geq 3$ in ACT total score at month 6

Endpoint
Percentage of patients with an increase from baseline $\geq 3$ in ACT total score at Month 6 (Visit 10)
Model Specification
This endpoint will be analysed using a logistic regression model. Only the month 6 (visit 10) data will be included in the model. Month 1 (visit 5) data will not be implemented since by this timepoint participants may not have reverted to steady medicating behaviour.
Terms in the model: 
 
• Dependent variable: Increase from baseline of <math>\geq 3</math> in ACT total score at month 6 responder/non-responder (binary score)
 
• Covariates:           
 
○ Categorical: randomised treatment arm, gender and country
 
○ Continuous: baseline ACT total score and age.
 
 
 

Patients who have a missing ACT total score at month 6 (visit 10) (i.e. no ACT data on-treatment) will be classified as non-responders at that visit.
Computation of confidence intervals for the odds ratios is based in the individual Wald tests.
Model Checking & Diagnostics
If the likelihood maximisation algorithm fails to converge due to complete or quasi-complete separation of the data then Firth's penalized likelihood ( Firth , 1993) will be implemented by use of the FIRTH option on the MODEL statement in PROC LOGISTIC.
The fit of the logistic regression model will be assessed by examining the ROC curve and other diagnostic plots

Model Results Presentation
The number and percentage of participants with a response within each randomised treatment arm will be presented by visit, together with the adjusted odds ratio comparing CIS Arms 1, 2, 3, 4 with Arm 5, associated 95% CIs and p-values.

